1.3.5. Overall Benefit/Risk Assessment

Currently the only available treatment for RSV is supportive care for infants and children requiring hospitalization. Based on the available data and proposed safety measures, the overall risk/benefit assessment for this study is acceptable for the following reasons:

- Continued careful study of the safety and PK is done in this study as well as evaluation of the preliminary efficacy of lumicitabine as an antiviral treatment for RSV.
- No safety concerns have previously been raised based on the safety information from healthy adult subjects and most observed AEs and laboratory abnormalities were mild to moderate in severity and considered not related to lumicitabine by the investigator (see Section 1.1, Background).
- Safety concerns have been raised based on the safety data from adult and pediatric subjects infected with RSV (see Section 1.1.2, Information on the Product, Subsection Clinical Studies). To reduce risk to subjects:
 - An IDMC will be established to monitor data in an unblinded manner on a regular basis to ensure the continuing safety of the subjects enrolled in this study.
 - JNJ-63549109 plasma target exposures for human subjects will be limited to a maximum average AUC_{0-24h} of 20,000 ng.h/mL (or 25,200 ng.h/mL in whole blood) for any given dose. This threshold provides safety margins that are at least 2.7-fold lower than the lowest systemic NOAEL exposure obtained in nonclinical toxicity studies.

- Several safety measures have been proposed to minimize potential risk and stress to subjects, including:
 - Only subjects who meet all of the inclusion criteria and none of the exclusion criteria (as specified in the protocol) will be allowed to participate in this study. The selection criteria include adequate provisions to minimize the risk and protect the well-being of subjects in the study.
 - Subjects are to be hospitalized upon treatment initiation allowing for intensive monitoring.
 - Close monitoring of subjects throughout the study (see Section 17.9, Monitoring).
 - Customary measures taken by investigational staff to ensure that study-specific assessments such as blood sampling are performed with as little additional stress as possible for the subject.
 - Utilization of data obtained from standard of care samples.
 - Safety surveillance will be performed in a manner that minimizes the total number of required invasive procedures (eg, blood draws) to minimize discomfort to study subjects. Laboratory monitoring of hematologic parameters is included as a safety assessment in all clinical studies with lumicitabine. Careful follow-up by the investigators and the sponsor study physician with frequent oversight by the study-specific IDMCs will continue as planned.
 - Utilization of discontinuation and withdrawal criteria (see Section 10.2, Discontinuation of Study Treatment/Withdrawal From the Study).

2. OBJECTIVES, ENDPOINTS, AND HYPOTHESIS

2.1. Objectives and Endpoints

2.1.1. Objectives

Primary Objective

The primary objective is to determine in hospitalized infants and children who are infected with RSV the dose-response relationship of multiple regimens of lumicitabine on antiviral activity based on nasal RSV shedding using qRT-PCR.

Secondary Objectives

The secondary objectives are to determine in hospitalized infants and children who are infected with RSV:

- The safety and tolerability of lumicitabine.
- The PK of JNJ-63549109 in whole blood.
- The impact of lumicitabine on the clinical course of RSV infection.
- The impact of lumicitabine on the duration and severity of signs and symptoms of RSV infection as assessed by the Pediatric RSV Electronic Severity and Outcome Rating System (PRESORS) questionnaire completed by the clinician in the electronic clinical outcome assessment (eCOA) device.

- The impact of lumicitabine on the time to undetectable nasal RSV viral load.
- The impact of lumicitabine on the emergence of RSV strains with resistance-associated mutations.
- The relationship between the PK of JNJ-63549109 and the PD (antiviral activity, clinical symptoms, and selected safety parameters) after single (LD) and repeated oral dosing (MD) of lumicitabine.
- The acceptability and palatability of the lumicitabine formulation.

Exploratory Objectives

The exploratory objectives are to evaluate in hospitalized infants and children who are infected with RSV:

- The relationship between viral load and clinical outcome, including the relationship between RSV RNA levels and:
 - Requirement for and duration of supplemental oxygen.
 - Time to hospital discharge or readiness for hospital discharge, with readiness for discharge as evaluated by the investigator.
 - Time to clinical stability defined as the time from initiation of study treatment until the time at which the following criteria are met: return to pre-RSV infection status (hereafter referred to as “normalization”) of blood oxygen level (without additional requirement of supplemental oxygen compared with pre-RSV infection status), normalization of oral feeding, normalization of respiratory rate, and normalization of heart rate.
- The relationship between viral load and duration and severity of signs and symptoms of RSV infection as assessed by the PRESORS questionnaire completed by the clinician in the eCOA device.
- The impact of the baseline viral subtype and genotype on the antiviral activity.
- The impact of lumicitabine on the duration and severity of signs and symptoms of RSV infection as assessed by the PRESORS questionnaire completed by the subject’s parent(s)/caregiver(s) in the eCOA device.
- The relationship between the clinician eCOA and parent(s)/caregiver(s) eCOA responses.
- Medical resource utilization.
- The impact of lumicitabine on the infectious viral load using a quantitative culture of RSV (plaque assay) may be performed in a central laboratory at timepoints selected by the virologist.
- The comparison of the RSV viral loads measured in the mid-turbinate nasal swabs and endotracheal samples from intubated subjects.

2.1.2. Endpoints

Primary Endpoint

The primary endpoint is RSV viral load (measured by qRT-PCR in the mid-turbinate nasal swab specimens) AUC from immediately prior to first dose of study drug (baseline) until Day 7.

Secondary Endpoints

The secondary endpoints are:

- Safety/tolerability including AEs, physical examinations, vital signs/peripheral capillary oxygen saturation (SpO₂), ECGs, and clinical laboratory results.
- PK parameters of JNJ-63549109.
- RSV clinical course endpoints:
 - Length of hospital stay from admission to discharge and to readiness for discharge and from study treatment initiation to discharge and to readiness for discharge, with readiness for discharge evaluated by the investigator.
 - Requirement for and duration of intensive care unit (ICU) stay.
 - Requirement for and duration of oxygen supplementation/noninvasive mechanical ventilation support (eg, nasal cannula, face mask, continuous positive airway pressure) and/or invasive mechanical ventilation support (eg, endotracheal-mechanical ventilation or mechanical ventilation via tracheostomy) above pre-RSV infection status.
 - Time to no longer requiring supplemental oxygen above pre-RSV infection status.
 - Time to clinical stability defined as the time from initiation of study treatment until the time at which the following criteria are met: return to pre-RSV infection status (hereafter referred to as “normalization”) of blood oxygen level (ie, without additional requirement of supplemental oxygen compared with pre-RSV infection status), normalization of oral feeding, normalization of respiratory rate, and normalization of heart rate.
 - Time from initiation of study treatment until SpO₂ ≥93% on room air among subjects who were not on supplemental oxygen prior to the onset of respiratory symptoms.
 - Time to respiratory rate, SpO₂, and body temperature return to pre-RSV infection status.
 - Incidence of acute otitis media (defined by the investigator).
- The duration and severity of signs and symptoms of RSV infection as assessed by the PRESORS questionnaire completed by the clinician in the eCOA device.
- RSV viral load as measured by qRT-PCR in the mid-turbinate nasal swab specimens, which will be used to determine the following:
 - RSV viral load over time.

- Peak viral load, time to peak viral load, rate of decline of viral load, and time to RSV RNA being undetectable.
- Proportion of subjects with undetectable RSV viral load at each timepoint.
- RSV viral load AUC from immediately prior to first dose of study drug (baseline) until Day 10 and until Day 14.
- RSV viral load AUC in subjects assigned to a longer dosing duration, if dosing duration is increased by the IDMC, from baseline until 1 day (+2 days) after the last dose of study drug.
- Sequence changes (postbaseline) in the RSV polymerase L-gene and other regions (if warranted) of the RSV genome compared with baseline sequences.
- Acceptability and palatability of the lumicitabine formulation as assessed by the parent(s)/caregiver(s) eCOA.

Exploratory Endpoints

The exploratory endpoints of this study are:

- The duration and severity of signs and symptoms of RSV infection as assessed by the PRESORS questionnaire completed by the parent(s)/caregiver(s) in the eCOA device.
- Number of hours the subject's parent(s)/caregiver(s) missed from usual activities.
- Medical resource utilization.
- RSV infectious viral load as measured using a quantitative viral culture (plaque assay).
- RSV viral load as measured by qRT-PCR of mid-turbinate nasal swabs and endotracheal samples in intubated subjects.

Refer to Section 9, Study Evaluations, for evaluations related to endpoints.

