4. SUBJECT POPULATION

Screening for eligible subjects will be performed as soon as possible following admission to the ER or hospitalization, such that subjects are randomized within 5 days of RSV symptom onset. Special attention will be paid to determine the duration of RSV symptoms from onset till time of randomization as accurately as possible. Male or female infants and children ≥ 28 days to ≤ 36 months of age diagnosed with RSV infection based on a PCR-based diagnostic assay (with or without coinfection with another respiratory pathogen) who have been (or will be) admitted to the hospital and whose parents have signed informed consent will be enrolled. Subjects who were admitted to the hospital for another reason but develop an acute respiratory illness while being hospitalized are also eligible for screening.

The inclusion and exclusion criteria for enrolling subjects in this study are described in the following 2 subsections. If there is a question about the inclusion or exclusion criteria below, the investigator must consult with the appropriate sponsor representative and resolve any issues before enrolling a subject in the study. Waivers are not allowed.

For a discussion of the statistical considerations of subject selection, refer to Section 11.2, Sample Size Determination.

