4.2. Exclusion Criteria

Any potential subject who meets any of the following criteria will be excluded from participating in the study:

1. Subjects who are not expected to survive for more than 48 hours.
2. Subjects who have had major thoracic or abdominal surgery in the 6 weeks prior to randomization.

3. Subjects who received (within 12 months prior to screening) or who are currently on a waiting list for a bone marrow, stem cell, or solid organ transplant, who received radiation or chemotherapy (within 12 months prior to screening), or who are currently taking immunosuppressive medication (refer to Section 8, Pre-study and Concomitant Therapy).
4. Subjects who have a known or suspected immunodeficiency (except immunoglobulin A [IgA] deficiency), such as a known human immunodeficiency virus infection.
5. Subjects who have a history of or concurrent illness (beyond a defined comorbid condition for severe RSV disease) that in the opinion of the investigator, might confound the results of the study or pose an additional risk in administering study drug to the subject, or that could prevent, limit, or confound the protocol-specified assessments such as liver or renal insufficiency; significant cardiac, vascular, pulmonary, gastrointestinal, endocrine, neurologic, hematologic, rheumatologic, metabolic disturbances, or genetic diseases that result in immunosuppression. These may include, but are not limited to bacteremia, organ dysfunction, or other severe comorbidities.
6. Subjects who have a poorly functioning gastrointestinal tract (ie, unable to absorb drugs or nutrition via enteral route).

NOTE: The use of IV fluids is not exclusionary so long as the investigator believes the subject's gastrointestinal tract still functions properly (ie, is able to absorb drugs or nutrition).
7. Subjects being treated with extracorporeal membrane oxygenation.
8. Subject receiving chronic oxygen therapy at home prior to admission.
9. Subjects who have taken any disallowed therapies as noted in Section 8, Prestudy and Concomitant Therapy, before the planned first dose of study drug.

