Requirement for supplemental feeding/hydration	
Does the subject require supplemental feeding/hydration (e.g. IV catheter/nasogastric tube) after first dose of study drug?
 
Categories will be Yes (1) or No (0).
 
Only derive this parameter for subjects that didn't require supplemental feeding/hydration before first dose of study drug.

Time to end of intensive care	The time from first study drug intake until the time of

Measurement	Formula
unit (ICU) stay (hours) [Time-to event]	
discharge from the ICU after which the subject was not readmitted to the ICU (= event)
 
Subjects who complete or withdraw from the study prior to the event will be censored at the date of completion or withdrawal. If the time is not available they will be censored at 12:00. In case of death the subject will be censored at the maximum observed number of hours until the occurrence of the event or censoring for all subjects achieving the event or being censored because of study completion or withdrawal. If no admittance to the ICU was necessary, the value will be set to 0.
 
(Date and time of event or censoring - date and time of first dose of study drug)/3600, rounded to one decimal

Time to end of Oxygen supplementation (hours) [Time-to event]	
The time from first dose of study drug start of oxygen supplementation to the last end date and time of any oxygen supplementation (= event) in hours (Oxygen supplementation is indicated on the Oxygen Supplementation form: Type of supplemental oxygen administration.). (Note: it is not necessary that the subject started on oxygen at baseline.)
 
If the end date is missing, the end date is considered to be after study completion or withdrawal.
 
Subjects who complete or withdraw from the study prior to the event will be censored at the date of completion or withdrawal. If the time is not available they will be censored at 12:00. In case of death the subject will be censored at the maximum observed number of hours until the occurrence of the event or censoring for all subjects achieving the event or being censored because of study completion or withdrawal.
 
If no oxygen supplementation was necessary after first dose of study drug, the value will be set to 0 hours.
 
(Date and time of event or censoring - date and time of first dose of study drug)/3600, rounded to one decimal

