Time to end of noninvasive mechanical ventilation support (hours) [Time-to event]	
The time from first dose of study drug to the last end date and time of noninvasive mechanical ventilation and invasive mechanical ventilation support (= event) in hours. Noninvasive mechanical ventilation and invasive mechanical

Measurement	Formula
	
ventilation are defined as indicated on the Oxygen Supplementation form: Type of supplemental oxygen administration.
 
Derivation similar as “Time to end of Oxygen supplementation”

Time to end of invasive mechanical ventilation support (hours) [Time-to event]
	
The time from first dose of study drug to the last end date and time of invasive mechanical ventilation support (= event) in hours. Invasive mechanical ventilation support is defined as indicated on the Oxygen Supplementation form: Type of supplemental oxygen administration.
 
Derivation similar as “Time to end of Oxygen supplementation”

Time to end of supplemental feeding/hydration (hours) [Time-to event]
	
The time from first dose of study drug to the last end date and time of supplemental feeding/hydration (e.g. IV catheter/nasogastric tube) (= event) in hours.
 
Derivation similar as “Time to end of Oxygen supplementation”

Time to return to pre-RSV disease level for respiratory rate (hours) [Time-to event]
	
The time from first dose of study drug until the time to return to pre-RSV disease level. The return to pre-RSV disease level occurs when the observed value of the parameter is indicated by the investigator as normal, and no later observed values are indicated by the investigator as abnormal (=event).
 
Normalization of respiratory rate (RR) will be derived from the answer to the corresponding question in the questionnaire “is this Respiratory Rate value normal for this patient?”
 
If no deterioration from pre-RSV disease levels occurred, the time will be set to time of first dose of study drug and the value will be set to 0 hours.
 
Subjects with an abnormal value at the last assessment will be censored at that time. Subjects for which this last assessment is the baseline assessment will be censored at time 0.

Measurement	Formula
	(Date and time of event or censoring - date and time of first dose of study drug)/3600, rounded to one decimal

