Time to return to pre-RSV disease level for heart rate (hours) [Time-to event]	
Idem as Time to return to pre-RSV disease level for respiratory rate (hours) but for heart rate.
 
Normalization of heart rate (HR) will be derived from the answer to the corresponding question in the questionnaire “is this Pulse value normal for this patient?”

Time to clinical stability (hours) [Time-to event]	
The time from first dose of study drug until the time at which the each of the following criteria are met (=event):
 
 • Normalization of Oxygen supplementation (as in parameter Time to end of Oxygen supplementation), • Normalization of feeding/hydration (as in parameter Time to end of supplemental feeding/hydration) , • Normalization of respiratory rate (as in parameter Time to return to pre-RSV disease level for respiratory rate), and • Normalization of heart rate (as in parameter Time to return to pre-RSV disease level for heart rate). 
In case any of the four components is censored, the time to clinical stability will also be censored at the first time-point of the censored component.
 
Subjects who complete or withdraw from the study prior to the event will be censored at the date of completion or withdrawal. If the time is not available they will be censored at 12:00. In case of death the subject will be censored at the maximum observed number of hours until the occurrence of the event or censoring for all subjects achieving the event or being censored because of study completion or withdrawal.
 
(maximum(Date and time of event criteria or censoring) - date and time of first dose of study drug)/3600, rounded to one decimal

Time to return to pre-RSV disease level for body temperature (hours), [Time-to event]	
The time from first dose of study drug until the time to return to pre-RSV disease level. The return to pre-RSV disease level occurs when the observed value of the parameter is within the normal range (=event).
 
If no deterioration from pre-RSV disease levels occurred, the

Measurement	Formula										

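### The SAP times the end of oxygen and ventilation support from zero support rather than from the child's pre-RSV level, which misstates recovery for the probably few eligible children who had support before RSV

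*Protocol*

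**What the plan says.** **Protocol, section 2.1.2.** The oxygen endpoint is "Time to no longer requiring supplemental oxygen above pre-RSV infection status". Requirement for and duration of oxygen, non-invasive and invasive support carry the same qualifier, down to "mechanical ventilation via tracheostomy) above pre-RSV infection status". Clinical stability, here and in section 11.3, asks for no oxygen need beyond the child's pre-RSV need. The SpO2-on-room-air endpoint is confined to children who were not on supplemental oxygen before respiratory symptoms began.

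**SAP, section 5.3.1.3.** Time to end of oxygen supplementation runs "to the last end date and time of any oxygen supplementation (= event) in hours". Time to end of invasive ventilation runs "to the last end date and time of invasive mechanical ventilation support (= event) in hours", and the non-invasive row is built in the same way. Clinical stability takes its oxygen component from the first of these: "Normalization of Oxygen supplementation (as in parameter Time to end of Oxygen supplementation". The room-air SpO2 row has no population limit.

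**Eligibility.** Protocol section 4.2 excludes a "Subject receiving chronic oxygen therapy at home prior to admission". Section 4 adds: "Subjects who were admitted to the hospital for another reason but develop an acute respiratory illness while being hospitalized are also eligible for screening". Comorbidities such as bronchopulmonary dysplasia and neuromuscular impairment are allowed, and no criterion bars ventilation at home.

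**The concern.** The protocol asks when a child is back to his or her own usual level of support. The SAP asks when all support of that type has stopped. For a child whose usual level was zero, these are the same question. For a child with support before RSV, the SAP records recovery too late or not at all.

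The effect carries into time to end of oxygen, of non-invasive and of invasive support, and into time to clinical stability. Those variables feed stratified Gehan tests, p-values combined by Liptak's method, and a Cox model for clinical stability (SAP 5.3.2.3). A recovered child scored as unrecovered adds a long time that has nothing to do with treatment. One or two such children would weigh most in the smaller ventilation sets.

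**Working it through.** No power or sample-size figure in the plan bears on this point, so there is none to reproduce. The check compares the definitions and then follows individual children through them.

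| Item | Protocol 2.1.2 | SAP 5.3.1.3 |
|---|---|---|
| End of oxygen | need back to pre-RSV level | last end of any oxygen |
| End of ventilation | duration above pre-RSV level | last end of that support |
| Clinical stability, oxygen part | no need beyond pre-RSV | as end of oxygen |
| Requirement | above pre-RSV level | new use, only in children not on that support before first dose |
| SpO2 on room air | only children not on oxygen before symptoms | all children |

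**Child 1: no support before RSV.** The pre-RSV level is zero, so both definitions give the same time. Exclusion criterion 8 puts most children here.

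**Child 2: on temporary oxygen in hospital for another reason when RSV began.** Suppose the child is back to that earlier oxygen level at time *a* and comes off oxygen at a later time *b*, before study end. The protocol's event is at *a* and the SAP's at *b*, so the SAP is late by *b* − *a*.

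**Child 3: on chronic ventilation without home oxygen, continuing to study end.** The protocol's event is at *a*. Under the SAP, support with no end date is taken to end after the study, and the child is censored at completion. With first dose on Day 1 and completion on Day 28, that is (28 − 1) × 24 = 648 h. The ±2-day visit window gives 25 × 24 = 600 h to 29 × 24 = 696 h. One censored component also censors clinical stability, so the child is never counted as stable. The form lists ventilation among the types of supplemental oxygen administration, so this child can enter the oxygen row too.

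**Step-ups.** The requirement rows exclude by tier:
- A child on oxygen only at first dose is left out of the oxygen row but stays in both mechanical-ventilation rows.
- A child on non-invasive mechanical ventilation stays in the invasive row.
- A move to a higher ventilation tier is therefore counted. An increase within the same tier is not.

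**Room air.** A child on oxygen before symptoms who stays on it is outside the protocol's population. The SAP includes that child and censors at the last SpO2 assessment.

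**How many.** The documents do not say. If every chronically supported child is comorbid, the 20% comorbidity cap bounds that group at 0.20 × 120 = 24 to 0.20 × 180 = 36, apart from the extra comorbid children allowed at 24 to 36 months. The lower end is 0. The true number is probably far below the bound, because chronic home oxygen is excluded. The cap does not bound children supported in hospital for other reasons.

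**Consistency within the SAP.** Section 1.1 keeps the pre-RSV comparison in its definition of clinical stability. The respiratory-rate and heart-rate rows use the investigator's view of what is normal for that child. Only the support components become absolute.

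**The case against.** The other side has real weight.

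- **Few children are affected.** Excluding chronic home oxygen makes the oxygen definitions agree for nearly everyone and makes the room-air restriction largely automatic. Children in hospital for another reason must also be medically stable apart from RSV or a listed comorbidity (inclusion 5) and pass exclusions 2 and 5. This stands.
- **The form is not shown.** If the Oxygen Supplementation form records only support above the usual level, no child is misclassified. This stands as a condition on the finding. The SAP does not say so.
- **The SAP is to be read with the protocol, and protocol 11.3 leaves normalization criteria to the SAP.** This helps only in part. Section 11.3 states the pre-RSV comparison in the definition itself and delegates how normalization is judged. A programmer working from the SAP row would code the last end of any support.

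Three stronger readings are tempting and are not supported:

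- **That such children can never have the event.** This is so only when support lasts to study end. Temporary in-hospital support that stops earlier gives a late event.
- **That any step-up in these children is lost.** Only a step-up within the same tier is.
- **That the power loss is large.** The documents give no input for it. Suppose 36 children per arm on oxygen, a 72 h placebo median, a time ratio of 0.65, a log-SD of 0.7 and four affected children per arm. An unstratified Gehan test then falls from about 71% to 50% power. SAP 5.3.2.3 specifies a stratified test, and comorbidity is a randomization stratum. With 7 comorbid children per arm and the affected children among them, the fall is from about 70% to 58% or from 67% to 62%, depending on how strata are weighted. Four per arm would also be half of the comorbid children allowed at 40 per arm (0.20 × 40 = 8). All these inputs are assumed, so the figures show only how strongly the answer depends on them.

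**Conclusion.** The concern holds in a limited form. SAP 5.3.1.3 does not implement the protocol's reference level for the oxygen and ventilation endpoints or for the oxygen component of clinical stability. It also omits the population limit on the room-air SpO2 endpoint. For most children this changes nothing. For those already supported in hospital when RSV began, or chronically ventilated without home oxygen, it gives a late event or censoring at completion.

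The conclusion about individual children assumes that the form records their usual support. The mismatch in definitions does not depend on that. The number affected is unknown and probably small, no power loss can be derived from the documents, and the primary viral-load analysis is untouched. It is still worth correcting, because the written rule gives the wrong event time for eligible children.

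**What to change.** In SAP 5.3.1.3:

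1. Define the end of oxygen, of non-invasive and of invasive support, and the oxygen component of clinical stability, as the last time support exceeds the child's pre-RSV level.
2. Define requirement as an increase above that level, so that a step-up within a tier counts.
3. Limit time to SpO2 of at least 93% on room air to children not on supplemental oxygen before symptom onset, as the protocol states.
4. State whether the Oxygen Supplementation form records unchanged usual support.

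Identify pre-RSV support from medical history before unblinding. Deciding afterwards who was back to usual would be open to influence from the results.

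The cost is SAP wording, programming and a medical-history check for a few children.
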